**b. External Location[s]:**

- APT Foundation, Inc.  Haskins Laboratories
- Connecticut Mental Health Center  John B. Pierce Laboratory, Inc.
- Veterans Affairs Hospital, West Haven  Other Locations, Specify: CMU

**c. Additional Required Documents (check all that apply):**  N/A

\*YCCI-Scientific and Safety Committee (YCCI-SSC) Approval Date:

\*Pediatric Protocol Review Committee (PPRC) Approval Date:

- \*YCC Protocol Review Committee (YRC-PRC) Approval Date:
- \*Dept. of Veterans Affairs, West Haven VA HSS Approval Date:
- \*Radioactive Drug Research Committee (RDRC) Approval Date:
- YNHH-Radiation Safety Committee (YNHH-RSC) Approval Date:
- Magnetic Resonance Research Center PRC (MRRC-PRC) Approval Date:
- YSM/YNHH Cancer Data Repository (CaDR) Approval Date:
- Dept. of Lab Medicine request for services or specimens form

*\*Approval from these committees is required before final HIC approval is granted. See instructions for documents required for initial submission and approval of the protocol. Allow sufficient time for these requests. Check with the oversight body for their time requirements.*

2. **Probable Duration of Project:** State the expected duration of the project, including all follow-up and data analysis activities. 5 years
3. **Targeted Enrollment:** What is the number of subjects: 86 non-treatment-seeking, alcohol-dependent, family history positive heavy drinkers
  - a. targeted for enrollment at Yale for this protocol? 86 participants  
If this is a multi-site study, what is the total number of subjects targeted across all sites?
  - b. expected to sign the consent form? 172
  - c. expected to complete some or all interventions for this protocol? 86
4. **Research Type/Phase: (Check all that apply)**

**a. Study Type**

- Single Center Study
- Multi-Center Study

Does the Yale PI serve as the PI of the multi-site study? Yes  No

- Coordinating Center/Data Management
- Other:

**b. Study Phase**  N/A

- Pilot
- Phase I
- Phase II
- Phase III
- Phase IV
- Other (Specify)

**c. Area of Research: (Check all that apply)** Note that these are overlapping definitions and more than one category may apply to your research protocol. Definitions for the following can be found

in the instructions section 4c:

- Clinical Research: Patient-Oriented  Clinical Research: Outcomes and
- Clinical Research: Epidemiologic and Behavioral  Health Services
- Translational Research #1 ("Bench-to-Bedside")  Interdisciplinary Research
- Translational Research #2 ("Bedside-to-Community")  Community-Based Research

5. Is this study required to be registered in a public database? Yes  No   
If yes, where is it registered?  
Clinical Trials.gov registry   
Other (Specify)
6. Will this research study utilize clinical care services at Yale New Haven Hospital or YMG?  
Yes  No

If yes, might these be billable to the subject, the sponsor, grant or other third party payer?

Yes  No

If you answered "yes", please register this study in the IDX/GE system at

<http://www.yalemedicalgroup.org/pfs/forms/10000/NewStudyRequest.pdf>

7. Are there any procedures involved in this protocol that will be performed at YNHH or one of its affiliated entities? Yes  No  *If Yes, please answer questions a through c and note instructions below. If No, proceed to Section III.*

a. Does your YNHH privilege delineation currently include the **specific procedure** that you will perform? Yes

b. Will you be using any new equipment or equipment that you have not used in the past for this procedure? No

c. Will a novel approach using existing equipment be applied? No

If you answered "no" to question 7a, or "yes" to question 7b or c, please contact the YNHH Department of Physician Services ([name]) for prior approval before commencing with your research protocol.

## SECTION V: RESEARCH PLAN

1. **Statement of Purpose:** State the scientific aim(s) of the study, or the hypotheses to be tested.

Development of new and effective strategies to treat alcoholism should be based on our understanding of the behavioral and neurochemical mechanisms mediating alcohol reward and drinking. Initiation and progression of alcohol-seeking behaviors involve complex interactions in the cortico-striatal circuitry between neurotransmitters like dopamine and opioids that signal reward in the nucleus accumbens and engage stimulus response habits in the dorsal striatum, as well as glutamatergic projections from the prefrontal cortex and basolateral amygdala to the nucleus accumbens that are involved in the reinstatement of alcohol drinking.

In HIC # 9912011476 and HIC # 0602001068, we examined the independent roles of dysfunctions in the glutamatergic and opioidergic circuits in mediating alcohol-drinking behaviors, using an alcohol drinking paradigm (ADP) for heavy drinkers developed by our group (O'Malley, Krishnan-Sarin et al., 2002). Using an NIH funded grant in HIC # 9912011476, we showed for the first time that the opioid antagonist naltrexone (NTX) significantly reduced drinking in drinkers with a positive family history (FH) of alcoholism (FHP; Krishnan-Sarin et al., 2007) but increased drinking in those without a FH of alcoholism (FHN), with no consistent changes in alcohol craving and stimulation. Similarly, interim analyses from HIC # 0602001068 indicate that the glutamate (NMDA) antagonist memantine (MEM) significantly reduced alcohol stimulation and craving with emerging, modest reductions in drinking (Krishnan-Sarin et al., 2009a) in FHP drinkers, with no consistent changes in FHN drinkers. This exciting evidence provides the first demonstration of distinctive roles for the glutamatergic and opioidergic systems in FHP drinkers; specifically, blocking opioid receptors with NTX appears to reduce stimulus response habits and alcohol drinking, while blocking NMDA receptor function with MEM appears to reduce alcohol reward.

In the current proposal we would like to conduct an important extension of this work. We will test the hypothesis that by targeting both opioidergic and glutamatergic mechanisms, one may synergistically target multiple neurochemical and behavioral processes, leading to optimal reduction of alcohol drinking. This pilot trial will be conducted in FHP drinkers in whom we have observed reduction in alcohol reward with MEM and in alcohol drinking with NTX. We will test the efficacy and tolerability of the combined use of MEM and NTX. We will also test the efficacy and tolerability of the combined use of N-acetyl cysteine and NTX. N-acetylcysteine (NAC), an acetyl pro-drug of cysteine is another agent which can be used to target the glutamatergic system. NAC is believed to produce its effects by stimulating the cysteine-glutamate exchanger and thus altering synaptic glutamate levels. A significant potential advantage of NAC is better tolerability, which may make it a better glutamate-altering agent to use in combination with NTX. Finally, we will also evaluate the predictive utility of impulsive responding, implicit alcohol motivational tendencies, and variations in genes for opiate receptors and for signal transduction proteins linking dopamine and glutamate receptors upon alcohol drinking behaviors.

The following specific aims will be tested:

**Primary Aim 1:** Evaluate the effects of pretreatment with a combination of naltrexone (NTX; 50 mg) and memantine (MEM; 20 mg) or N-acetylcysteine (NAC; 2400 mg) on drinking in FHP drinkers.

*Primary Hypothesis:* Combination treatment with NTX and MEM or NAC, when compared with NTX alone, will reduce number of drinks consumed during the self-administration period.  
*Exploratory hypothesis:* Combination treatment with NTX and MEM will reduce time to first drink and increase the average time to consume each drink, during the self-administration phase.

**Primary Aim 2:** Evaluate the effects of pretreatment with a combination of naltrexone (NTX; 50 mg) and memantine (MEM; 20 mg) or NAC (2400 mg) on alcohol craving in FHP drinkers  
*Hypothesis:* Combination treatment with NTX and MEM or NAC, when compared with NTX alone, will reduce alcohol craving (Yale Craving Scale) during the self-administration period  
*Exploratory hypothesis:* Combination treatment with NTX and MEM will reduce craving in response to the alcohol cue presented just prior to the priming drink period.

**Primary Aim 3:** Evaluate the effects of pretreatment with a combination of naltrexone (NTX; 50 mg) and memantine (MEM; 20 mg) or NAC (2400 mg) on alcohol-induced stimulation in FHP drinkers.

*Hypothesis:* Combination treatment with NTX and MEM or NAC, when compared with NTX alone, will reduce alcohol-induced stimulation (Biphasic Alcohol Effects Scale) during the self-administration period.

**Secondary Aim:** Examine the tolerability of co-administration of NTX and MEM and NTX and NAC

**Exploratory Aims:** Examine the influence of innovative predictors of treatment response, including:

- ❖ Impulsive propensity and implicit alcohol associations
- ❖ Opioidergic (OPRM1) and signal transduction proteins that moderate the function of NR2B-containing NMDA receptors (Fyn kinase, STEP) genotypes
- ❖ Pavlovian to Instrumental transfer propensity

2. **Background:** Describe the background information that led to the plan for this project. Provide references to support the expectation of obtaining useful scientific data.

Alcohol use, abuse, and dependence are a huge public health problem in the United States and worldwide. Epidemiological evidence suggests that almost 17.6 million adults in the U.S. are abusing alcohol or are alcohol dependent (Grant et al., 2004), emphasizing the importance of developing optimal interventions for the treatment of this disorder. At present, three medications have been approved by the FDA in the U.S. for the treatment of alcohol dependence: disulfiram, naltrexone, and acamprosate. However, the treatments effects for these agents range from minimal to modest, and they are minimally utilized in clinical community settings (Garbutt et al., 1999; Krishnan-Sarin et al., 2009b). Therefore, there is a significant need for other medications, or combinations of medications, that are more efficacious in reducing alcohol use.

A cornerstone to the development of pharmacotherapy to reduce alcohol drinking rests in a detailed understanding of the neurotransmitters involved in mediating alcohol's effects. Alcohol influences a variety of neurotransmitters, such as opioids, dopamine, serotonin, gamma amino butyric acid, and glutamate, and each one of these neurotransmitter systems has been shown to play a role in many of alcohol's effects, including but not limited to alcohol reinforcement, craving, and withdrawal (Krishnan-Sarin et al., 2009; Krystal and Tabakoff, 2002). While most clinical trials have focused on single pharmacological agents with single mechanisms of action,

the above evidence suggests that it would be important to investigate the efficacy of combining drugs that influence multiple neurotransmitter systems. In fact the development of combination therapies that have minimal side effects and can be used to produce optimal reductions in alcohol drinking in habitual drinkers by targeting different behaviors is a major priority of treatment development (e.g., Kranzler, 2000).

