- b. *Priming dose (PD) period:* The PD of alcohol that is provided at 3 pm will contain a dose of 80 proof alcohol designed to raise blood alcohol levels to 0.03 mg% of alcohol, and subjects will have 5 minutes to drink it. The purpose of the PD is to provide a standard dose for evaluating the effects of medications on the responses to a standard drink of alcohol and to model a "lapse" situation.
- c. *Absorption Period and Ratings of Ethanol Effects:* A 50-minute absorption period will follow during which the subjective and physiological effects of this priming dose of alcohol in combination with memantine will be monitored. Using this procedure, we will be able to closely monitor changes in subjective effects (alcohol craving, stimulation/sedation) during the rising and falling limbs of the blood alcohol curve.
- d. *Alcohol self-administration (SA) periods:* Following the PD, participants will be exposed to three one-hour SA periods designed to model a "relapse" situation. During each SA period they will be permitted to drink up to four alcoholic drinks designed to raise BALs by 0.015 mg% of alcohol, or to receive cash (equivalent to the price of each drink that is not consumed). The first SA period will begin at 4 pm, when the research assistant will take 4 prepared drinks into the room along with a "tab" sheet worth \$12. The participant will be informed that these 4 drinks will be available to him/her for the next 60 minutes (i.e., until 5 pm). S/he can choose either to drink or to keep the money; each drink will cost \$3. For example, if the participant chooses to drink only one drink in the next one hour, s/he will earn \$9. The money will be given to them the next morning before they leave the hospital. The second and third SA periods will begin at 5 pm and 6 pm, respectively, and will be similar to the SA period. Thus, participants can choose to consume up to 12 additional drinks over this 3-hour period or to receive up to \$36 to take home the next morning.

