- g) *Biphasic Alcohol Effects Scale (BAES)*(Martin et al., 1993): This 14 item self-report, adjective rating scale will be used to measure the stimulant and sedative effects of alcohol during the priming dose on Day 7. This instrument has been found to be sensitive to memantine and naltrexone's effects on alcohol intoxication (pilot date, Kranzler et al., 2000; Reynolds et al., 2004; Swift et al., 1994).
- h) *Childhood Trauma Questionnaire* (Bernstein, et al. 1994): This 28-item self-report inventory that provides brief, reliable, and valid screening for histories of abuse and neglect. It inquires about five types of maltreatment - emotional, physical, and sexual abuse, and emotional and physical neglect. Also included is a 3 item Minimization/Denial scale for detecting false-negative trauma reports.
- i) *Drinking Motives Questionnaire (DMQ)*(Cooper et al. 1992): contains 15 reasons why people might be motivated to drink alcoholic beverages. Participants rate on a 4-point scale how frequently each of the 15 listed reasons motivate them to drink alcoholic beverages. The measure yields three scale scores reflecting different motives for drinking alcohol.
- j) *Brief Self-Control Scale (Tangney et al., 2004)*: provides a rapid brief assessment of self-control and regulation.
- k) *Sensitivity to Punishment and Sensitivity to Reward Questionnaire (SPSRQ)*(Torrubia et al., 2001): consists of 48 yes-no items that included questions about habitual behaviours in response to cues of punishment, frustrative non-reward and novel stimuli as well as stimuli related to reward and approach-related tendencies.
- l) *The Self-Report Habit Index (SRHI)* (Verplanken & Orbell, 2003).: a 12-item index of habit strength developed on the basis of features of habit; that is, a history of repetition, automaticity (lack of control and awareness, efficiency), and expressing identity.
- m) *UPPS Impulsive Behavior Scale* (Whiteside & Lynam, 2003): a 45-item self-report questionnaire which distinguishes four facets of impulsivity: urgency, lack of premeditation,

lack of perseverance, and sensation-seeking. It is scored on a 4-point scale from Strongly Agree to Strongly Disagree.

Laboratory Measures:

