**Aim 1:** Total number of drinks consumed during the self-administration period will be compared among treatment conditions using linear mixed models with treatment (NTX vs. NTX+MEM/NAC) included as a within-subjects factor. In these models, we will also consider baseline drinking, as assessed by using the 90 day TLFB obtained at intake, as a potential covariate. Non-significant covariates will be dropped for parsimony. A significant treatment effect, where total number of drinks is reduced during combination NTX+MEM/NAC treatment compared to NTX alone, will be supportive of our hypothesis. Secondary measures of alcohol-drinking typology such as average time to consume each drink and inter-sip interval will be analyzed using similar models as described above, whereas time to first drink during the ad-lib drinking period will be analyzed using survival models with subject-specific frailties to account for correlation of the repeated survival outcomes within individuals.

**Aim 2:** Scores on the Yale Craving Scale will be the primary outcome in this aim and will represent the dependent variable in a linear mixed model evaluating combination treatment effects of NTX and MEM/NAC on alcohol craving. The model will include treatment (NTX vs. NTX+MEM/NAC) and time (see study time points, Table 1) as within-subjects explanatory factors, and random subjects effects. The interaction between treatment and time will be modeled and interpreted using graphical displays and appropriate post-hoc tests. We anticipate a significant treatment by time interaction explained by greater reductions in craving over time among combination NTX+MEM/NAC compared to NTX alone. A secondary measure of craving, the Alcohol Urge Questionnaire, will be analyzed using the same model described above. We will also explore the influence NTX vs. NTX+MEM/NAC on YCS alcohol craving in response to the alcohol cue exposure just prior to the start of the priming drink period using a similar model.

**Aim 3:** Alcohol-induced stimulation, measured by the Biphasic Alcohol Effects Scale (BAES), will be analyzed using the same model described for alcohol craving in Aim 2. A significant treatment by time interaction, explained by reduced alcohol stimulation to due to combination

NTX+MEM/NAC treatment, compared to NTX alone, will be supportive of our hypothesis. A secondary analysis will conduct similar comparisons on the sedation scores obtained using the BAES.

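### The Aim 3 rule cannot tell a weaker stimulant response to alcohol from simply drinking less, because no fixed-dose contrast is pre-specified

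*Combined protocol and SAP*

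**What the plan says.** The Primary Aim 3 hypothesis in Section V.1 is that combination treatment "will reduce alcohol-induced stimulation (Biphasic Alcohol Effects Scale) during the self-administration period", relative to naltrexone alone. The Primary Aim 1 hypothesis, for the same window, is that the combination "will reduce number of drinks consumed during the self-administration period".

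Section V.4 (Statistical Considerations) analyses the Biphasic Alcohol Effects Scale (BAES) with the Aim 2 craving model. Its terms are treatment "and time (see study time points, Table 1) as within-subjects explanatory factors, and random subjects effects", plus the treatment-by-time interaction, which "will be modeled and interpreted using graphical displays and appropriate post-hoc tests". The criterion for support is "A significant treatment by time interaction, explained by reduced alcohol stimulation to due to combination" treatment. Neither drinks consumed nor blood alcohol is in the model.

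The Alcohol-Drinking Paradigm section describes two kinds of alcohol exposure. The priming dose at 3 pm is the same nominal dose for everyone; part of its purpose is "to provide a standard dose for evaluating the effects of medications on the responses to a standard drink of alcohol". From 4 pm the dose is self-chosen: "participants can choose to consume up to 12 additional drinks over this 3-hour period". The Assessments section says the BAES "will be used to measure the stimulant and sedative effects of alcohol during the priming dose on Day 7". The same part of Section V.3 says blood alcohol can be correlated with subjective effects, but the Aim 3 analysis does not take this up.

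**The concern.** Treatment cannot alter the alcohol dose before 4 pm; after 4 pm it can. Suppose the combination reduces drinking and leaves the stimulant response to a given amount of alcohol untouched. The BAES ratings up to 3:50 pm are then the same under both treatments. If stimulation rises with alcohol level, the later ratings are lower on the combination. That is a treatment-by-time interaction in the supportive direction, and it comes from Aim 1's effect alone.

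This matters because the Statement of Purpose presents reduced drinking (naltrexone) and reduced alcohol reward (memantine) as separate actions. A positive Aim 3 could be reported as evidence of the second when it partly or wholly restates the first. The Power Analysis section describes a pilot that will supply effect-size estimates for later trials, so it matters which effect the Aim 3 estimate represents.

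The stated windows also differ. Section V.1 puts the Aim 3 outcome in the self-administration period, the Assessments section ties the BAES to the priming dose, and Section V.4 names no window.

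**Working it through.** **Ratings available.** Table 1 schedules the BAES at 2:00 and 2:30 pm (before alcohol); 3:10, 3:30 and 3:50 pm (after the priming dose); 4:30, 4:55, 5:30, 5:55, 6:30 and 7:00 pm (self-administration); and 8, 9 and 10 pm. That is 2 + 3 + 6 + 3 = 14 ratings. Of the 12 taken after alcohol, 9 depend on self-chosen intake. The nominal self-chosen dose runs from 0 to 12 × 0.015 = 0.18 g/dl, on top of 0.03.

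**Plan's own figure.** There is none for Aim 3. The Power Analysis gives 30 completers, 10 per group (3 × 10 = 30), with no effect size, SD or power. What follows is illustration.

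**Assumptions, not from the documents.** Stimulation is linear in nominal alcohol level; elimination is ignored; there is no direct drug effect on stimulation; the response to the priming dose is 0.25, 0.5 or 1.0 residual SD; the 11 ratings to 7 pm are used; forgone drinks are spread evenly over 4 to 7 pm.

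**Alcohol deficit.** For two fewer drinks the deficit at hour *t* is 2 × 0.015 × (t − 16)/3. At the six self-administration ratings this gives 0.0050, 0.0092, 0.0150, 0.0192, 0.0250 and 0.0300 g/dl. The mean is 0.0172, and 0.0172/0.03 = 57% of the priming dose. For one fewer drink the mean is 0.0086, or 29%.

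**Interaction test.** Noncentral F with λ = n(Cd)′[2CRC′]⁻¹(Cd). Here d is the vector of treatment differences in residual SD, C holds the 10 contrasts against the first rating, and R is the identity or ρ^(gap in half hours). df1 = 10, df2 = 21(n − 1), α = 0.05. Probability that the test rejects, for priming-dose responses of 0.25 / 0.5 / 1.0 SD:

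| Fewer drinks | Pairs | ρ = 0 | ρ = 0.5 | ρ = 0.7 |
|---|---|---|---|---|
| 2 | 30 | .093 / .276 / .901 | .072 / .156 / .601 | .070 / .145 / .553 |
| 2 | 20 | .077 / .185 / .709 | .064 / .114 / .401 | .063 / .108 / .365 |
| 2 | 10 | .062 / .107 / .359 | .057 / .078 / .195 | .056 / .076 / .179 |
| 1 | 30 | .060 / .093 / .276 | .055 / .072 / .156 | .055 / .070 / .145 |

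**Fixed-dose contrast.** Take the mean of the three post-priming ratings minus the mean of the two pre-drink ratings, compared between treatments by a paired t test. Drinking less cannot move it. In 20,000 simulated trials (30 pairs, two fewer drinks, 1.0 SD response) it rejected in 5.0%, 4.8% and 5.2% for ρ = 0, 0.5 and 0.7. Its SE is √(2c′Rc/n). At ρ = 0 and n = 30, c′c = 1/3 + 1/2 = 0.833 and SE = √(1.667/30) = 0.236, so the 95% CI half-width is 2.045 × 0.236 = 0.48 SD. Across the three correlations the half-width is 0.48–0.54 SD at 30 pairs and 0.92–1.04 SD at 10.

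**Second model.** A separate simulation used all 14 ratings, elimination of 0.015 g/dl per hour, subject-by-treatment variance (SD 3), residual SD 6, and slopes of 100 or 200 BAES points per g/dl. With intake lower by one to three drinks and no change in response per unit of alcohol, the interaction rule was met in 6% to 53% of trials at 10 pairs and 11% to 97% at 30. The priming-dose contrast stayed at 4% to 6%. With no change in drinking, both tests stayed at about 5% to 6%.

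**The case against.** **The rule matches the hypothesis.** Section V.1 asks about stimulation during self-administration, and a total effect is a legitimate answer. This stands as far as it goes, and the total effect should be kept. But the hypothesis speaks of stimulation induced by alcohol, the rationale separates reward from drinking, and the priming dose was included to hold the dose fixed. The total effect does not answer that question.

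**The plan partly handles it.** The priming-dose ratings appear to be levels of time through Table 1, and graphs or post-hoc tests could show a gap that opens only after 4 pm. True: the limit lies in the rule, not in the data. But no such test is named, and none is required before support is claimed.

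**The bias depends on an assumed form.** The documents give no dose–stimulation slope. If stimulation followed the rate of rise instead, so that two forgone drinks removed a constant 17–33% of a 1.0 SD priming response, the same formula gives about 7–24% at 30 pairs and 6–10% at 10. This lowers the size, not the direction.

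**Prior data suggest a small bias.** Sections V.1 and V.2 report that naltrexone reduced drinking in family-history-positive drinkers without consistent change in stimulation or reward. That is a fair reason for restraint. The dose justification for memantine, however, says 20 mg reduced stimulation and also seemed to reduce drinking, so the two effects may occur together.

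**Thirty pairs is the best case.** Each participant has two medication periods for three conditions. If the three pairings were balanced, only 20 of 30 completers would supply a naltrexone-alone comparison, 10 per combination. This stands, and the smaller figures should be read alongside the larger.

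**The replacement contrast is weak.** Also true. In the second simulation it had only 6% to 17% power for a 30% fall in response at equal intake.

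**Conclusion.** The concern holds. As written, a significant Aim 3 interaction does not distinguish a smaller stimulant response to alcohol from lower intake, and the plan requires nothing further before support is claimed. This follows from the text and the timing of the ratings, given only that stimulation rises with alcohol exposure.

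The size cannot be determined from the documents. For two fewer drinks and no direct drug effect on stimulation, the linear illustration ranges from barely above the nominal 5% (about 6% at 10 pairs with a weak priming response) to 90% (30 pairs, 1.0 SD response, independent residuals). With serial correlation the upper figure falls to 55–60%. If drinking does not change there is no inflation. The change should be made because it is cheap and settles what the estimate means, not because a large bias has been shown.

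**What to change.** 1. In Section V.4, pre-specify from the existing model the treatment contrast in BAES stimulation at 3:10, 3:30 and 3:50 pm relative to 2:00 and 2:30 pm. Base any claim of a reduced stimulant response to alcohol on it. Report it with a 95% CI, and state that a non-significant result at pilot size is not evidence of no effect.
2. Keep the self-administration outcome, labelled as a total effect that includes drinking less.
3. Treat any analysis adjusted for blood alcohol as supportive only. It conditions on a variable affected by treatment, and Table 1 has no blood alcohol at 4:30, 5:30 or 6:30 pm.
4. State how the added contrast enters the Bonferroni count in Section V.4.
5. Reconcile the BAES window across Section V.1, the Assessments section and Section V.4. As a clerical matter, also reconcile Day 7 in the BAES description with Day 6 in the entries on videotaped drinking and blood alcohol.

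The cost is protocol and SAP wording; the five ratings are already scheduled. The price is one more named contrast, at a lower alcohol level and with only three post-dose ratings, so an effect present only at higher levels would appear only in the self-administration outcome. Precision is limited: under the linear model's residual assumptions, 80% power needs a difference of about 0.68–0.77 residual SD at 30 pairs, or 1.28–1.44 at 10.
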